3.3 OUTCOME MEASURES

The primary endpoints are firstly the cut-off of the serum Neurotensin and IL-8 values selected by the ROC curves and the demonstrated estimate of area under ROC curve (accuracy) in predicting colorectal cancer and colorectal adenomas.

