1.8 THE NEED FOR A TRIAL

Colorectal cancer mortality can be lowered by both early diagnosis and cancer prevention.[1, 2] The objective of screening is to detect cancer at an early, curable stage. Individuals at average risk, those older than 50 years of age, with a negative family history and negative history of adenoma, colorectal cancer, or inflammatory bowel disease are among the highest yield group.

Recent literature proposes that after an initial negative colonoscopy (which is the current standard of screening not only in average risk but also in increased risk patients, should start at age 50 or earlier age with frequency depending on risk factors: e.g. personal/family history of polyps/cancer, inflammatory bowel disease, known genetic syndrome and prior colonoscopy findings), follow-up with rescreening after the age of 60 with annual guaiac fecal occult blood testing, annual fecal immunochemical testing, or computed tomographic colonography every five years provides approximately the same benefit in life-years with fewer complications and at a lower cost.[3] There is a lack of consensus concerning the use of CT colonography as a primary screening tool.

The number of CRC cases from colorectal cancer screening is still rather low. Sensitivity of guaiac tests for the detection of CRC/adenomas is 21.8%-46.3%.(4) Colonoscopy is the favoured screening method for individuals at average risk despite lower patient compliance with this modality. A meta-analysis of 14 randomized controlled trials documented that although endoscopic surveillance was superior to stool testing in detecting advanced neoplasms, its benefit was eclipsed by a lower participation rate.[4] Colonoscopy is the favored screening method for individuals at average risk despite lower patient compliance with this modality. Whilst colonoscopy is an outstanding tool for diagnosing potentially curable bowel cancer, too many patients are currently having an unnecessary procedure as the pick-up rate for bowel cancer is only 4%. Nevertheless, NCCN guideline panelists agree that any form of screening is better than none.[5]

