3.1 CONTROL(S) / COMPARATOR(S)

All individuals fulfilling the inclusion criteria will be enrolled. After the refinement of participants by the exclusion criteria blood sample will be drawn for Neurotensin and IL-8. Following the report of colonoscopy and the histology individuals will be assigned in three groups: a) group A - cancer patients, b) group B – adenoma (polyp) patients and c) group C – No pathology/normal colonoscopy. Two primary analyses will be conducted to define the cut-off plasma values for Neurotensin and IL-8 for a) diagnosing cancer (group A versus group C) and b) diagnosing adenomas (group B versus group C). A secondary analysis will be conducted comparing the performance of the Neurotensin/IL-8 system towards the 2-weeks referral and FOB test positive patients for the diagnosis of colorectal cancer and adenomas.

The reason for using participants without bowel pathology is because we need to define the "normal range" of Neurotensin and IL-8 serum values.

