3.5 PROPOSED SAMPLE SIZE / POWER CALCULATIONS

Assuming that the AUC of the new test is commensurate with the pilot study (AUC=0.85), we calculate the number of samples required to obtain a 95%

confidence interval of size 0.1. We assume that the ROC curve follows a binormal distribution, and that the prevalence of adenoma/cancer is between 20-30% in the study participants. We obtain that we require between 400 (30% prevalence) and 553 (20% prevalence) participants. We therefore target an enrollment of 500 patients. We intend to perform an interim analysis after 50% of the patients have been included and evaluated.

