4.2 Exploratory analysis of secondary endpoints

Adenoma frequency and other qualitative characteristics: H0: p1=p2 is tested against the alternative H1: $p1 \neq p2$.

The diagnostic performance of the proposed biomarker system of Neurotensin and IL-8, will be assessed against the current screening system with 2-weeks referral/FOB test by using propensity scoring in binary logistic regression.

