5.5 What will happen at the end of our study?

After our study has ended and If the outcomes of our study are promising for detecting colorectal adenomas and cancer, an effort will be to conduct a multicentre study. The results will be fed back to participants according to their wish.

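### Cut-offs are chosen from this study's ROC curves and, as written, judged in the same patients; under common optimising rules this biases sensitivity upward, by an amount the protocol leaves open

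*Protocol*

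**What the plan says.** Section 3.1 assigns participants after colonoscopy and histology to cancer (A), adenoma (B) or no pathology (C), and states: "Two primary analyses will be conducted to define the cut-off plasma values for Neurotensin and IL-8". There is one analysis for cancer (A against C) and one for adenoma (B against C). Section 3.3 lists "the cut-off of the serum Neurotensin and IL-8 values selected by the ROC curves" as a primary endpoint, together with the AUC.

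Section 2.1.1 describes the system through its cut-offs: colonoscopy if neurotensin is low, or if neurotensin is high and IL-8 is also high. Sections 3.1 and 4.2 add a secondary comparison in which this system "will be assessed against the current screening system with 2-weeks referral/FOB test", "by using propensity scoring in binary logistic regression".

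The pilot cut-offs (neurotensin at or below 54.47 pg/ml, IL-8 at or above 8.83 pg/ml) appear in 2.1.1 only as background. The protocol names no hold-out sample, and section 3.4 on bias mentions only matching. Section 5.5 says that a multicentre study would be attempted "If the outcomes of our study are promising for detecting colorectal adenomas and cancer".

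**The concern.** A cut-off that maximises a criterion in a sample partly follows that sample's chance features. Sensitivity read at that cut-off in the same patients is then too high on average. Fewer cases mean more bias, so cancer is affected more than adenoma. The 2-week/FOB pathway is not tuned to these data, so any comparison made at the selected cut-offs would give the biomarkers an advantage that the pathway does not have.

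Two things are at stake. One is the sensitivity that readers would take from the study into the judgement in 5.5. The other is the cut-off itself, a primary endpoint, which is poorly determined when cancers are few. The sample size in 3.5 does not protect against either: it targets the precision of an AUC, with adenoma and cancer pooled.

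**Working it through.** **1. The plan's own figure.** Inputs from 3.5: AUC 0.85, binormal ROC, 95% interval of full width 0.1 (half-width 0.05), pooled prevalence 20% to 30%. The Obuchowski variance is V = 0.0099·exp(−a²/2)·[(5a² + 8) + (a² + 8)/k], with a = 1.414·z(AUC) = 1.4655, a² = 2.148, and k = non-cases per case. Cases needed = 1.96²·V/0.05².

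- 20% prevalence, k = 4: V = 0.0720, cases = 110.6, total = 110.6/0.20 = 553.
- 30% prevalence, k = 2.33: V = 0.0781, cases = 120.0, total = 120.0/0.30 = 400.

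Both stated totals (553 and 400) reproduce. They concern AUC, which does not depend on any cut-off.

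**2. Inputs for the cut-off question.**

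- AUC 0.85 and the binormal form: section 3.5. The pilot IL-8 AUC of 0.81: section 2.1.1.
- Cancers: not stated for this study. The only cancer rate is in 1.8, which says of current colonoscopy practice that "the pick-up rate for bowel cancer is only 4" per cent. Assumption: 0.04 × 500 = 20.
- Non-cases: 500 × 0.70 = 350 at 30% pooled prevalence; 400 at 20%.
- Selection rule: not stated. Assumption: maximum Youden index, with alternatives in step 4.

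**3. Simulation, one marker.** Controls are N(0,1) and cases N(d,1), with d = √2·z(0.85) = 1.466. In each simulated study the cut-off maximising sensitivity plus specificity is chosen. Apparent sensitivity is then compared with true sensitivity at that cut-off. There were 4,000 or more runs per setting.

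| Cases / controls | Apparent sensitivity | True sensitivity | Inflation (points) |
|---|---|---|---|
| 10 / 350 | 85.3% | 71.9% | 13 |
| 20 / 350 | 82.3% | 73.7% | 9 |
| 30 / 370 | 81.0% | 74.3% | 7 |
| 50 / 350 | 80.4% | 75.5% | 5 |
| 100 / 400 | 79.3% | 76.1% | 3 |
| 150 / 350 | 78.4% | 76.2% | 2 |

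At AUC 0.81 with 20 cancers the inflation is about 9 points. Ten cancers is what 4% gives at the 250-patient interim look. Specificity is inflated by at most about 1 point. With 20 cancers, the central 95% of chosen cut-offs correspond to true specificities from about 57% to 93%.

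**4. Other selection rules, 20 cancers, AUC 0.85.** Closest to the corner: about 7 points. Sensitivity equal to specificity: about 0.5. Specificity fixed at 90%: about 0.

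**5. Two-marker rule, 20 cancers, markers assumed independent.** With each cut-off chosen separately, apparent sensitivity is 96.5% against a true 92.1%, about 4 points. With both chosen jointly it is 89.2% against 74.7%, about 14 points.

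**6. How much resampling recovers.** In the 20/350 Youden setting (500 runs, 200 bootstraps), bootstrap correction moved mean sensitivity from 82% to 76% against a true 73%. That removes (82 − 76)/(82 − 73) = about two-thirds of the optimism. The percentile 95% interval for the cut-off covered the true optimum about 86% of the time.

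**The case against.** The strongest reply is that the size is not the protocol's own. A reader might infer that the plan overstates cancer sensitivity by 9 points. The documents do not support that as a plain statement. It needs a Youden rule that is not written down. It needs 20 cancers, taken from a background rate, in a cohort whose inclusion criteria also mention bowel-habit change and two positive FIT/FOB tests. And it is a one-marker figure, whereas the pathway comparison concerns two markers. At the pooled 100 to 150 cases of 3.5 the inflation is only 2 to 3 points. All of this stands, and the size has to be given as a range.

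A reader might also infer that the comparison in 4.2 favours the biomarkers by construction. That goes too far. Section 4.2 is headed exploratory and specifies a logistic regression; it does not say whether the markers enter as continuous values or split at the cut-offs. The bias applies to any comparison made at the selected cut-offs. Likewise, 5.5 sets no sensitivity threshold, so the documents do not show that the multicentre decision would rest on sensitivity. The study calls itself a pilot in section 2, and a later study could test the cut-offs afresh, although 4.1 is headed confirmatory.

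Finally, the selection rule and the correction could sit in an analysis plan that is not shown. This stands in part. But the protocol itself fixes that the cut-offs are derived here and that the system they define is assessed here, so its endpoint and comparison wording should point to corrected figures.

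**Conclusion.** The point holds as a design weakness of conditional size. As written, the cut-offs are derived and the system assessed in the same patients, and the pilot cut-offs are not tested as fixed thresholds. Under common optimising rules, sensitivity at the selected cut-offs is biased upward.

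The inflation is about 9 points for one marker with a Youden cut-off, AUC 0.85 and about 20 cancers. With that number of cancers it runs from near 0 to about 14 points, depending on the rule and on whether one or two markers are used. For one marker under Youden it falls to about 3 points with 100 cases, so the adenoma analysis is much less affected if adenomas make up most of the pooled cases. AUC is unaffected. The spread of true specificity, 57% to 93%, rests on the same Youden, one-marker, 20-cancer assumptions and is reason enough to report the cut-off with an interval. This should be changed, but it does not undermine the AUC endpoint.

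**What to change.** In 3.3, 4.1 and 4.2:

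- Name the rule by which the cut-offs are selected.
- Report sensitivity and specificity at the selected cut-offs, for each marker and for the two-marker rule, corrected for optimism by bootstrap or repeated cross-validation. Re-select the cut-offs in every resample.
- Give each cut-off a bootstrap 95% interval.
- Use the corrected figures for any cut-off-based comparison in 4.2 and for the judgement in 5.5.
- Also report the performance of the pilot cut-offs (54.47 and 8.83 pg/ml) as pre-specified thresholds. They carry no such optimism in these patients, provided the assays are comparable. That has to be confirmed, since 2.1.1 describes the pilot values as plasma and this study stores serum.

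The cost is protocol wording and slightly more analysis work, with no new samples. The headline sensitivity will be less favourable. The correction reduces the optimism but does not fully remove it when cancers are few, and the report should say so.

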3.4 METHODS AGAINST BIAS

We will apply population controls matched by gender, age, BMI and ethnic background.

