1.4 STUDY TYPE

Case control study

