3.2 INCLUSION / EXCLUSION CRITERIA

3.2.1 Inclusion criteria:

Individuals over 50 years of age referred for colonoscopy under any indication.

Over 60 years of age,

Change in bowel habit to looser/more frequent stools,

+/- PR bleeding AND

2 positive FIT/FOB tests.

3.2.1 Exclusion criteria:

a) Need for emergency surgery,

b) Presence of Inflammatory bowel disease,

c) Known history of inherited colorectal cancer,

d) History of cancer in another primary site,

e) Presence of liver metastases (Neurotensin is metabolized in the liver),

f) Negative previous colonoscopy for cancer,

g) Haemolysis in serum samples,

h) Informed consent not signed/withdrawal and

i) Persons who will not have the capacity to decide for

themselves, who are unable to represent their own interests or are particularly susceptible to coercion.

Information concerning performance status, use of statins, steroids or any

anti-inflammatory / immunosuppressive medications will also be collected.

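### Section 3.4 promises matched population controls, but the design in 3.1 and the sample size in 3.5 rest on one colonoscopy cohort with every non-case as an unmatched control

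*Protocol*

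**What the plan says.** Section 3.4, the whole of the protocol's text on methods against bias, reads: "We will apply population controls matched by gender, age, BMI and ethnic background". It gives no source for these controls, no ratio and no matching method.

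Section 3.1 describes recruitment differently: "All individuals fulfilling the inclusion criteria will be enrolled". Blood is then drawn, and "Following the report of colonoscopy and the histology individuals will be assigned in three groups": cancer (A), adenoma (B) and normal colonoscopy (C). The two primary analyses are A versus C and B versus C. Group C has a further purpose: "The reason for using participants without bowel pathology is because we need to define the" normal range of the two markers. Section 3.2 gives the source population as "Individuals over 50 years of age referred for colonoscopy under any indication", followed by further age, symptom and stool-test criteria.

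Section 3.5 sizes the study on the width of the confidence interval for the AUC, with cancer/adenoma prevalence among participants of 20% to 30%. It arrives at 553 and 400 participants respectively and targets 500.

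Section 4.1 puts the same four covariates into a propensity score, refers in passing to a matching step and labels the groups as treatment and control. Section 1.4 gives the study type as "Case control study", while the title calls the study prospective.

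**The concern.** The two sections name different control groups for both primary analyses. Under 3.1, disease status is unknown when blood is taken, so nobody can be matched as a case or a control at recruitment. Controls are whoever turns out to have a normal colonoscopy. Under 3.4, they are a matched population set that no other section recruits, counts or examines.

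The cut-offs and the AUC are the primary endpoints (section 3.3), and both depend directly on who the controls are. Two analysts, one following 3.1 and the other 3.4, could use different control sets and report different primary results. The sample size can be consistent with only one of the two designs.

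**Working it through.** **Which design does section 3.5 assume?**

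Inputs from 3.5: AUC 0.85, 95% confidence, total interval width 0.1 (half-width 0.05), binormal ROC curve, prevalence 20% to 30%. The basis is "Assuming that the AUC of the new test is commensurate with the pilot study (AUC=0.85"), from which "we calculate the number of samples required to obtain a 95"% interval of that size.

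The protocol does not name its formula. The Obuchowski binormal variance was tried, with k controls per case:

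- V = 0.0099 × exp(−a²/2) × [(5a² + 8) + (a² + 8)/k], where a = 1.414 × z(0.85)
- cases needed = 1.96² × V / 0.05²; total = cases / prevalence
- z(0.85) = 1.0364, so a = 1.4655, a² = 2.1477, and V = 0.003383 × [18.739 + 10.148/k]

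With every non-case as a control, k = (1 − prevalence)/prevalence:

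- 30%: k = 2.33, V = 0.07810, cases = 120.0, total = 120.0/0.30 = 400.0 (stated: 400)
- 20%: k = 4, V = 0.07197, cases = 110.6, total = 110.6/0.20 = 552.9 (stated: 553)

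Both stated figures come back. The Hanley-McNeil variance gives 338 and 484 and does not reproduce them. So 3.5 assumes one cohort in which all non-cases serve as controls.

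**What would matching inside group C cost?**

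The ratio is not stated, so 1:1 and 1:2 are shown as assumptions. Cases pool cancer and adenoma, as 3.5 does, and non-cases are taken as group C. V is 0.09771 at k = 1 and 0.08055 at k = 2. Width = 2 × 1.96 × √(V / cases), with 100 cases (20%) or 150 cases (30%) among 500 participants.

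| Controls used | Width, 20% (100 cases, 400 non-cases) | Width, 30% (150 cases, 350 non-cases) | Controls unused (20%; 30%) | Enrolment for width 0.1 (20%; 30%) |
|---|---|---|---|---|
| All | 0.105 | 0.089 | 0%; 0% | 553; 400 |
| 1:2 | 0.111 | 0.091 | 50%; 14% | about 619; 413 |
| 1:1 | 0.123 | 0.100 | 75%; 57% | about 750; 500 |

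Unused shares: at 1:1, 300/400 and 200/350; at 1:2, 200/400 and 50/350. Enrolment at 1:1: 150.1 cases / 0.20 and / 0.30. At 1:2: 123.8 / 0.20 and / 0.30.

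**Cancer analysis (A versus C), illustration only.** Assume that the 4% cancer pick-up rate quoted in section 1.8 applies here, giving 0.04 × 500 = 20 cancers. Against 350 to 400 controls the width is about 0.22. At 1:1 (20 versus 20) it is 0.27, with about 94% to 95% of controls unused.

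**Three readings of 3.4, set against the other sections**

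- *External population controls.* No one is discarded, but the group is absent from 3.1, 3.2, 3.5 and 3.6, and no colonoscopy is described to confirm that its members are disease-free.
- *Matching within group C.* Every control is verified, but some go unused and 3.5 no longer applies as written. The matched controls take on the cases' age, sex and BMI mix instead of that of referred patients without pathology. Section 2.1.1 reports age as a marginal predictor of neurotensin (p = 0.059), so the cut-off and normal range could move. The protocol gives nothing from which to compute by how much.
- *Covariate adjustment only.* Nobody is dropped and 3.5 stands, but then 3.4 misdescribes the method.

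**The case against.** The strongest reply is that 3.4 is a loose description of the propensity methods in 4.1 and 4.2, which use the same four covariates and need not drop anyone. That is possible, but 4.1 itself mentions matching without saying what it does, so it does not settle the question. If adjustment is what was meant, the sentence in 3.4 is wrong as worded.

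A second reply is that the precision loss may be modest. This stands in part. At 1:2 and 30% prevalence the width moves only from 0.089 to 0.091, and even at 1:1 with 150 cases it is 0.100, which is the protocol's own target.

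A reader might infer several stronger points that the documents do not support:

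- *Matching would discard most controls.* For the pooled cases this holds at 1:1 (57% to 75%). At 1:2 the share is 14% to 50%, and under adjustment or external controls it is nil.
- *All the harms apply together.* Unverified controls belong to the external reading and lost controls to the within-cohort reading.
- *Predictive values could not be obtained, or prevalence loses its meaning.* If matching is nested in the cohort, prevalence is still known and can be combined with sensitivity and specificity. It also fixes how many cases 500 enrolments yield. Predictive values are not a stated primary endpoint.
- *The AUC would be biased by a known amount.* Matching changes the control population being described, which is partly a choice of estimand, and the size of the shift cannot be derived from the protocol.

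**Conclusion.** The contradiction stands. Section 3.4 names a control group that the design in 3.1 does not contain, and the sample size in 3.5 reproduces only with all non-cases as unmatched controls. This is a stated rule in conflict with the rest of the protocol, not a detail left for an analysis plan.

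If the rule were applied as matching within group C at 500 participants, the interval would widen from 0.105 to between 0.111 (1:2) and 0.123 (1:1) at 20% prevalence, and from 0.089 to between 0.091 and 0.100 at 30%. These figures rest on the protocol's AUC and prevalence, on pooling cancer with adenoma, and on matching ratios assumed here. The effect on the cut-off and normal range is a concern about which population group C would represent, and no size can be put on it.

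**What to change.** - **3.4:** replace the sentence with a statement that controls are all group C participants from the enrolled cohort, used unmatched in the primary AUC and cut-off analyses.
- **Covariates:** handle age, gender, BMI and ethnic background by adjustment, for example a covariate-adjusted ROC curve, as a supporting analysis.
- **1.4:** change the study type to a prospective diagnostic accuracy cohort. Do not add that patients are consecutive: the protocol does not say so, and 3.6 assumes 50% participation.
- **4.1:** remove or align the references to matching and to treatment and control groups. Otherwise the contradiction survives there.
- **If matching is kept:** state the source of the controls and the ratio, and redo 3.5.

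The recommended route changes wording only. It adds no procedure or participant and keeps the precision that 3.5 assumes. Keeping matching within the cohort at 1:1 would raise enrolment for a width of 0.1 to about 500 to 750.

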3.5 PROPOSED SAMPLE SIZE / POWER CALCULATIONS

Assuming that the AUC of the new test is commensurate with the pilot study (AUC=0.85), we calculate the number of samples required to obtain a 95%

confidence interval of size 0.1. We assume that the ROC curve follows a binormal distribution, and that the prevalence of adenoma/cancer is between 20-30% in the study participants. We obtain that we require between 400 (30% prevalence) and 553 (20% prevalence) participants. We therefore target an enrollment of 500 patients. We intend to perform an interim analysis after 50% of the patients have been included and evaluated.

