2.1 EVIDENCE

2.1.1 Serum neurotensin/IL-8 values in colorectal cancer

Serum neurotensin/IL-8 values in the diagnosis of colorectal cancer have been reported for first time in literature by our own group.[18, 19] This pilot study aimed to determine the feasibility of serum neurotensin/IL-8 values being used as a screening tool for colorectal cancer. Fifty-six patients and 15 healthy controls were assigned to seven groups according to their disease entity based on theater records and histology report. Blood samples for neurotensin and IL-8 were measured using an enzyme-linked immunosorbent assay.

There were no differences in the clinical and biochemical parameters of patients and controls. Group (p= 0.003) and age (p= 0.059: marginally significant) were independent predictors of neurotensin plasma values. Neurotensin (p= 0.004) and IL-8 (p= 0.029) differed between healthy and colorectal cancer patients. Neurotensin values differentiated the control group from all remaining groups.

The value of plasma neurotensin ≤54.47 pg/ml at enrollment selected by ROC curves demonstrated a sensitivity of 77%, specificity of 90%, and an estimate of area under ROC curve (accuracy) of 85% in predicting colorectal cancer.

At enrollment, the value of plasma IL-8 ≥8.83 pg/ml had a sensitivity of 85%, specificity 80%, and an estimate of area under ROC curve (accuracy) of 81% in predicting colorectal cancer.

Our results depicted that IL-8 should be used complementary to neurotensin due to its lower specificity. None of the colorectal cancer patients displayed a combination of high neurotensin and low IL-8 values (beyond cutoffs). Unpredictably, 3 out of 13 patients in the colorectal cancer group had neurotensin values above the cut-off value defined by the ROC curve. Notwithstanding, the IL-8 values of the same patients were high and well above the cut-off value, as our analysis anticipated for this group. Two other colorectal cancer group patients unexpectedly had low IL-8 values, but they also had low neurotensin values, as our analysis expected for this group. None of the colorectal cancer group patients displayed a combination of high neurotensin and low IL-8 values (which would be in contrast with our analysis).

Finally, one healthy control had a low neurotensin value as well as a low IL-8 value.

This pilot study[18] implicated that a blood neurotensin/IL-8 system may be used as a screening tool for colorectal cancer.

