4. STATISTICAL ANALYSIS

4.1 Confirmatory analysis of primary endpoints

In order to compare the low to high risk groups, the propensity score will be used that is the probability of a case being in a particular group based on a given set of covariates (e.g., age, gender, BMI and ethnic background). Generally, will be calculated using logistic regression with group (Treatment /Control) as dependent and covariates as independent variables. In order to deal with missing data in covariates, we will apply multiple imputation by either Separate creation of propensity scores from the matching or we will aggregate cases to get mean (median) propensity score. H0: p1=p2 is tested against the alternative H1: $p1 \neq p2$ using the exact Fisher tests.

A receiver operating characteristic (ROC) curve will be used to summarize the performance of the two-class classifiers (for Neurotensin and IL-8) for cancer and adenomas across the range of possible thresholds.

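### The sample size treats the neurotensin pilot AUC (0.85) as that of the whole test; by the same formula IL-8 (AUC 0.81) needs 465 to 637 rather than 400 to 553

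*Protocol*

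**What the plan says.** The calculation in Protocol section 3.5 rests on a single AUC: "Assuming that the AUC of the new test is commensurate with the pilot study (AUC=0.85"). The goal is a 95% "confidence interval of size 0.1". Two further assumptions follow: "We assume that the ROC curve follows a binormal distribution", and "the prevalence of adenoma/cancer is between 20-30% in the study participants". The result is 400 participants at 30% prevalence and 553 at 20%, and the enrolment target is 500.

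The pilot results are in section 2.1.1. For neurotensin the text reports "specificity of 90%, and an estimate of area under ROC curve (accuracy) of 85% in predicting colorectal cancer". For IL-8 it reports "specificity 80%, and an estimate of area under ROC curve (accuracy) of 81% in predicting colorectal cancer". No AUC appears for the two markers used together.

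Section 3.3 lists among the primary endpoints "the cut-off of the serum Neurotensin and IL-8 values selected by the ROC curves", with the AUC. Section 4.1, the confirmatory analysis, summarises by ROC curve the "performance of the two-class classifiers (for Neurotensin and IL-8) for cancer and adenomas". Section 3.1 defines two primary comparisons, cancer against normal colonoscopy and adenoma against normal colonoscopy, and seeks cut-offs for both markers in each.

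Section 2.1.1 also describes how the markers would be used. Neurotensin is read first, and IL-8 is a complementary second step for people whose neurotensin is high; it is not proposed as a screening marker on its own.

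**The concern.** In a precision-based calculation for an AUC, the assumed AUC sets the variance. Under the binormal model, 0.81 has a larger variance than 0.85. Section 3.5 therefore used the marker with the smaller requirement and described its value as that of the new test. A reader will take the 0.1 width as the planned precision for the primary analysis as a whole, when the stated figures support it for neurotensin only.

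The width of the interval is the only reason the protocol gives for n = 500. If the stated width does not cover one of the two markers in the primary analysis, that reason is incomplete.

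**Working it through.** **Inputs.** AUC 0.85 (section 3.5; neurotensin in section 2.1.1). AUC 0.81 (IL-8, section 2.1.1). Full width 0.1, so half-width 0.05, at 95% (section 3.5). Prevalence p of 20% to 30% (section 3.5); 25% is added here as the midpoint. Controls per case: k = (1 − p)/p, which is 2.333, 3 and 4 at 30%, 25% and 20%.

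**Formula.** The protocol names the binormal assumption but prints no formula. The usual binormal (Obuchowski) form is:

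- A = 1.414 × Φ⁻¹(AUC)
- V = 0.0099 × exp(−A²/2) × [(5A² + 8) + (A² + 8)/k]
- cases = 1.96² × V / 0.05²
- N = cases / p
- width at a given N = 2 × 1.96 × √(V / (N × p))

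**Step 1: reproduce the printed figures, AUC 0.85.** Φ⁻¹(0.85) = 1.0364, A = 1.4655, A² = 2.1477, exp(−A²/2) = 0.3417.

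- 30%: V = 0.0099 × 0.3417 × (18.739 + 10.148/2.333) = 0.0781; cases = 120.0; N = 400.0
- 20%: V = 0.0099 × 0.3417 × (18.739 + 10.148/4) = 0.0720; cases = 110.6; N = 552.9

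These are the printed 400 and 553. At 25% the same formula gives 460.

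**Step 2: change only the AUC, to 0.81.** Φ⁻¹(0.81) = 0.8779, A = 1.2413, A² = 1.5409, exp(−A²/2) = 0.4628.

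- 30%: V = 0.0099 × 0.4628 × (15.705 + 9.541/2.333) = 0.0907; cases = 139.4; N = 464.5
- 25%: V = 0.0865; cases = 133.0; N = 531.8
- 20%: V = 0.0829; cases = 127.4; N = 636.8

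The requirement rises by 15% to 16%.

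**Step 3: widths.**

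| Prevalence | Neurotensin, n = 500 | IL-8, n = 500 | IL-8 at the printed N |
|---|---|---|---|
| 30% | 0.089 | 0.096 | 0.108 (N = 400) |
| 25% | 0.096 | 0.103 | – |
| 20% | 0.105 | 0.113 | 0.107 (N = 553) |

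With n = 500 the width reaches 0.1 at a prevalence of about 22.6% for neurotensin and about 27.1% for IL-8.

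**Step 4: sensitivity to the variance formula, AUC 0.81.** The Hanley–McNeil variance needs 408, 475 and 578 at 30%, 25% and 20%, and gives widths of 0.090, 0.097 and 0.108 at n = 500. The exact Mann–Whitney variance under equal-variance normal markers needs 330, 370 and 433, and gives 0.081, 0.086 and 0.093. Simulated DeLong intervals under that same model also average 0.081 to 0.093. Neither alternative variance reproduces 400 and 553 at AUC 0.85: Hanley–McNeil gives 338 and 484, the exact form 260 and 340.

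**The case against.** **The protocol computes correctly from the input it states.** This stands. A reader might infer an arithmetic error, but 400 and 553 are right for AUC 0.85, and section 3.5 makes no explicit statement about IL-8. What is wrong is the label on the input, and that only one marker was covered.

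**IL-8 is secondary in the screening model.** A reader might infer that the two markers have equal standing throughout. Section 2.1.1 does not support that, and sizing on the lead marker could be defended. But section 3.5 does not say that it does so, and sections 3.1, 3.3 and 4.1 put the cut-offs and ROC curves of both markers in the primary analysis without ranking them. The two-step rule also needs an IL-8 cut-off.

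**The new test may mean the combination.** Possible, given the study title. But no combined AUC is reported, and 0.85 matches only neurotensin. On that reading the input would have no stated source.

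**The effect is small.** This stands. At 25% prevalence the miss is 0.003. At 20% neurotensin misses too, so choosing 500 over 553 already accepted an approximate target. The mid-range miss disappears under both alternative variances in the working. A reader might infer that IL-8 cannot be estimated usefully or that more patients are needed; neither follows.

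**The pilot hardly separates 0.85 from 0.81.** This is fair. With 13 colorectal cancer patients and 15 healthy controls, the Hanley–McNeil standard errors are about 0.077 and 0.085, so the gap of 0.04 is about half of one standard error. That is a further reason not to rest the calculation on the more favourable value alone.

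**Corrected figures could mislead in their turn.** This stands and shapes the fix. Both pilot AUCs are for cancer, while the 20% to 30% prevalence pools adenoma with cancer, which neither primary comparison does. As an illustration only, suppose the 4% pick-up rate in section 1.8 applied here (an assumption). Then 500 participants include about 20 cancers. With k = 24 the same formula gives widths of about 0.22 for neurotensin and 0.24 for IL-8.

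**Conclusion.** The point holds as a mislabelled and incomplete input to the sample size. Section 3.5 presents the neurotensin AUC as that of the test. By the formula that reproduces its own figures, the range for IL-8 is 465 to 637, and the target of 500 meets the 0.1 width for IL-8 only at a prevalence of about 27% or more.

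The size is modest: 15% to 16% more participants, or an interval wider by about 0.007 to 0.008 at n = 500. It rests on the pilot AUCs being the right planning values, on the protocol's pooled prevalence of 20% to 30%, and on a conservative binormal variance inferred from its exact match to the printed numbers.

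**What to change.** Keep n = 500 and revise section 3.5 as follows.

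- Label 0.85 and 400 to 553 as the neurotensin calculation.
- Add the IL-8 calculation: AUC 0.81, 465 (30% prevalence) to 637 (20%).
- Replace the single width of 0.1 with the expected width at n = 500 for each marker: 0.089 to 0.105 for neurotensin and 0.096 to 0.113 for IL-8, over 30% to 20% prevalence.
- State that these widths apply the pilot cancer AUCs to a pooled adenoma and cancer case group, and that they do not describe the separate cancer-versus-normal and adenoma-versus-normal primary analyses, which have fewer cases and wider intervals.

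The cost is the rewording of one paragraph and a slightly less favourable stated precision for IL-8. No extra participants or procedures are needed.
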